To assess the effectiveness of this multilevel intervention, called the workplace *Metabolic Health Improvement Program (MHIP)*, we will conduct a double-randomized trial in partnership with the clinical trials division of a large Northern California-based academic healthcare system, Sutter Health ($N=700$ employees on $N=16$ hospital campuses). We will first cluster-randomize 8 Sutter Health hospital campuses to the SSB sales ban condition and 8 campuses to serve as controls (no sales ban). Across these 16 campuses, we will further randomize heavy-SSB-consuming employees (>30 oz/week) to receive a brief SSB counseling intervention delivered remotely or to a control condition.^{11,12} The **primary outcomes** are central obesity (e.g., waist circumference) and change in serum insulin sensitivity (homeostatic model assessment [HOMA] ratio). **Secondary outcomes** include changes in SSB consumption, Body Mass Index (BMI), and lab values to include: lipid profile, triglycerides, triglyceride:HDL ratio, uric acid, ApoA, ApoB, lactate, ALT/AST, GGT, fasting glucose, fasting insulin, HbA1c. We will assess dietary composition remotely using the Automated Self-Administered 24-hour (ASA-24) at baseline, 6 and 12 months, and waist circumference remotely with empirically validated instructions and a standardized tape measure provided to participants. We will collect blood samples in the workplace labs at baseline and 12 months. All analyses will consider compensatory changes in at-home SSB intake, calories from sugar, and total calories. Aims are:

Aim 1: How well does each intervention work alone? We will assess the independent effects of the brief counseling intervention and workplace SSB sales ban on changes in primary and secondary outcomes. We will compare outcomes across employees exposed to the brief intervention only ($n=175$), SSB sales ban only ($n=175$), and no intervention ($n=175$). *We hypothesize that the brief counseling intervention and sales ban will each independently decrease waist circumference and HOMA relative to no intervention. Those at high risk (baseline BMI >25 , ethnic-minority, and lower-occupational status) will benefit more from the interventions.*

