Aim 2: Does a multilevel intervention work better? We will assess the effects of combining a brief intervention and SSB sales ban on outcomes. We will compare outcomes for participants exposed to the multilevel intervention ($n=175$) to those who receive the: (a) brief intervention only ($n=175$), (b)

**SUTTER HEALTH
INSTITUTIONAL REVIEW BOARD**

Protocol Summary Form

sales ban only ($n=175$), and (c) no intervention ($n=175$). *We hypothesize that the combined intervention will have a greater effect on outcomes than the brief intervention or sales ban alone. Higher-risk employees (see Aim 1) will benefit more from the multilevel intervention than their lower-risk counterparts.*

Aim 3: (Exploratory): How does the intervention work? We will test whether changes in SSB cravings mediate the effects of the multilevel intervention on outcomes. The multilevel intervention seeks to increase motivation to reduce SSB intake while reducing environmental cues to drink SSBs. *We hypothesize that the multilevel intervention will lead to the greatest reductions in cravings for SSBs, and cravings will mediate its effects on outcomes. We will explore mediation across high-risk groups (see Aim 1).*

2. BACKGROUND:

Obesity and type 2 diabetes are pressing health concerns, particularly for lower-income and ethnic minority employees. Obesity rates are at an all-time high and disparities persist: 49.6% of adult African Americans are currently obese and 44.8% of Latinos, compared to 42.2% of non-Hispanic whites.¹³ Diabetes rates have nearly doubled since 2000.¹⁴ Employers face disproportionately rising obesity-related healthcare costs alongside productivity losses.¹⁵ Obesity is major concern for occupational safety, particularly for physically active nurses, manual workers and technicians at heightened risk for injury.^{15,16}

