statistically significant mean reduction of 4.2 oz/day in SSB consumption in employees at intervention sites versus controls ($p < .04$), including a 2.7 oz/day reduction in SSBs consumed while at work ($p < 0.02$). *This study is not cluster-randomized nor does it consider serum biomarkers for metabolic disease, which the proposed study will address. However, it demonstrates a successful collaboration with Sutter Health, and shows the feasibility of the proposed recruitment and remote data collection efforts.*

3. SIGNIFICANCE:

The proposed study tests a scalable, efficient approach for obesity prevention in the workplace. Following recent trials demonstrating the effectiveness of online obesity counseling using nonmedical providers, we test a remote counseling intervention delivered by trained health coaches.^{38,39} The SSB sales ban is a food environment intervention that is easily adopted through changes in procurement policy and that promotes health equity by impacting the workforce as a whole.

Across all aims of the proposed study, we will assess the heterogeneity of intervention effects across higher-risk employee groups from ethnic minority backgrounds, lower occupational status and >25 baseline BMI. A recognized limitation of this study is that our disparities analyses will be confined to people in the workforce. If the interventions tested here prove effective, however, future studies can test them in other congregate settings that touch populations outside the labor market (e.g., in criminal justice settings, community colleges).

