Analytic Plan: We will analyze Aim 1 using all data collected at the baseline, 6- and 12-month time points. First, we will use ANOVA to compare group means and determine whether there is a significant main effect for each intervention (the sales ban and the brief intervention). Based on theory and our previous studies, we know that baseline risk factors and demographics are likely relevant to the impact of these interventions; those at greater baseline risk tend to benefit more from the interventions. Therefore, each dependent variable will also be examined using a linear regression model, which allows us to observe the main effects of these factors. For example, the model predicting HOMA change would include assignment to the sales ban condition (coded as 0/1), assignment to the brief intervention condition (coded as 0/1), baseline HOMA, baseline SSB consumption, baseline BMI, race/ethnicity, and sex. Subsequent models can consider baseline BMI > 25, ethnicity and job classification. The procedure for analyzing each outcome would be the same, but with each primary and secondary outcome substituted for HOMA in turn.

For SSB consumption, we will examine at-work consumption, at-home consumption, and total consumption as separate outcomes to thoroughly investigate the impact of the interventions across work and home environments. We will similarly check for potential compensatory consumption in sugar from calories and total calories for participants in the intervention conditions relative to controls. If ASA-24-based total calories or calories from sugar disproportionately increase in the intervention groups, this suggests a compensatory effect.

Although we believe our strategy of cluster randomization and controlling for individual differences that can vary regionally (such as ethnic distribution) is sufficient, we will also analyze the effects of the brief intervention via an exploratory mixed regression model, with individuals nested within sites, to see if study site was an important factor. If it is, we will consider mixed models where possible.

**SUTTER HEALTH
INSTITUTIONAL REVIEW BOARD**

Protocol Summary Form

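### The hypothesis that higher-BMI employees benefit more is framed only by a cut at BMI 25, with no intervention-by-BMI term written out; under a linear gradient the cut would lose roughly 36-57% of the information

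*Combined protocol and SAP*

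**What the plan says.** Aim 1 (section 1, Study Aim/Purpose) states the hypothesis: "Those at high risk (baseline BMI >25 , ethnic-minority, and lower-occupational status) will benefit more from the interventions". Aim 2 carries it over by reference to Aim 1, and the Aim 1 introduction in section (4c) extends it to the analyses for all aims. Section 3 (Significance) frames it the same way: "we will assess the heterogeneity of intervention effects across higher-risk employee groups from ethnic minority backgrounds, lower occupational status and >25 baseline BMI".

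The Aim 1 Analytic Plan in (4c) gives an example regression whose covariates are "baseline HOMA, baseline SSB consumption, baseline BMI, race/ethnicity, and sex". It describes the regression as one "which allows us to observe the main effects of these factors", and then adds: "Subsequent models can consider baseline BMI > 25, ethnicity and job classification". The listing of baseline BMI apart from BMI > 25 suggests that the first is continuous, but the plan does not say so.

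Under (4b), height and weight are measured on a standard scale with a stadiometer, so the full BMI value will exist. The only interaction written out for Aims 1 and 2 is sales ban by counseling, in the Aim 2 Analytic Plan. The power calculations cover the two main effects and that interaction. None covers modification by BMI.

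**The concern.** An indicator at 25 treats a participant at 25.1 like one at 40, and one at 24.9 like one at 19. If benefit rises gradually with BMI, the indicator throws away the gradient within each group. It also ties the answer to a single cut.

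The loss grows as the split becomes more uneven. The Background reports that "49.6% of adult African Americans are currently obese and 44.8% of Latinos, compared to 42.2% of non-Hispanic whites". If the enrolled employees resemble those populations, well over half would exceed 25 and the comparison group would be small.

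Tests of effect modification usually have less power than the main comparisons, so a further loss on a named hypothesis matters. The problem is separate from the missing product term: adding intervention by BMI > 25 would fill that gap and still leave the loss in place.

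**Working it through.** **Plan figure to reproduce.** There is none. The documents state no power or sample size for BMI modification, and give no BMI mean, SD or share above 25 for this sample.

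**Inputs.** N = 550 at 12 months and alpha .05 come from the Aim 1 Power Calculations (80% of 700 is 560; the plan uses 550). Alpha is taken as two-sided. Assumed: normal BMI, modification linear in BMI, share *p* above 25 between 50% and 85%, and a reference power of 80% for the continuous test. Site clustering is ignored.

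**Formulas.** With z_p the standard normal quantile at *p*, the fraction of information kept after the cut is RE = φ(z_p)² / [p(1−p)]. Power after the cut is Φ(2.80·√RE − 1.96), where 2.80 = 1.96 + 0.84 corresponds to 80% power before the cut.

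At p = 0.50: 0.3989² / 0.25 = 0.637; power Φ(2.80 × 0.798 − 1.96) = 0.608.

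At p = 0.85: 0.2332² / 0.1275 = 0.426; power Φ(2.80 × 0.653 − 1.96) = 0.448.

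| Share above 25 | Kept | Lost | 550 acts like | Power |
|---|---|---|---|---|
| 50% | 0.637 | 36.3% | 350 | 60.8% |
| 60% | 0.622 | 37.8% | 342 | 59.8% |
| 70% | 0.576 | 42.4% | 317 | 56.6% |
| 75% | 0.539 | 46.1% | 296 | 53.8% |
| 80% | 0.490 | 51.0% | 269 | 50.0% |
| 85% | 0.426 | 57.4% | 235 | 44.8% |

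RE is largest at p = 0.50, so with normal BMI and a linear gradient the loss is at least 36% whatever the share above 25.

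**Skewed BMI.** With lognormal BMI and SD 6, the loss is about 40%, 43%, 48%, 53%, 59% and 66% for means of 26, 27, 28, 29, 30 and 31. With normal BMI and the same means and SD, it is about 37%, 39%, 42%, 46%, 51% and 56%.

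**Shape of the modification.** A simulation of the interaction test (N = 550, lognormal BMI, mean 29, SD 6, 3,000 runs) gave:

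- linear gradient: 79% power with continuous BMI, 47% with the cut;
- true step at 25: 48% with continuous BMI, 80% with the cut.

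Other shapes can be compared under the same BMI distribution. Let r be the correlation between the true shape and the modifier used. Power is then Φ(2.80·r − 1.96), set to 80% when the true shape is modelled.

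| True shape | Continuous | Cut at 25 |
|---|---|---|
| Step at 27 | 56% | 54% |
| Step at 28 | 59% | 43% |
| Step at 30 | about 60% | 28% |
| Step at 35 | 52% | 11% |
| Flat to 25, then rising | 77% | 35% |
| Rising to 35, then flat | 76% | 58% |
| Rising to 30, then flat | 66% | 67% |

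The cut is clearly better only for a threshold at or very near 25. By a step at 27 the two are about level.

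**The case against.** The strongest reply is that the cut matches the hypothesis as worded. High risk is defined in advance as BMI above 25, and the Background reports a pilot result for that group. A contrast at 25 therefore answers the stated question directly, while a slope answers a related one. This stands as a reason to keep the contrast in the report. It does not make the contrast the better test, because the documents argue for no threshold at 25. The pilot, which the protocol itself calls underpowered, is also reported in opposite directions: those above 25 benefitted most in the Background, those below 25 in the Aim 1 introduction of (4c).

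It is also fair to say that the plan commits to little. A reader might infer that the cut is the fixed test of this hypothesis. The documents do not support that: the wording is permissive, the regression is described in terms of main effects, and no product term is given. The more basic gap is the unspecified modification test, and the loss applies to whatever test is later built on the indicator.

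A reader might also take 36-57% as an established loss for this trial. It is not, because normality, the share above 25 and linearity are all assumed. The obesity rates describe US adults by group, not employed heavy SSB drinkers at these hospitals. The 36% end requires exactly half the sample above 25. With a true step at 25 the comparison reverses.

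Finally, one added quadratic or spline term for BMI does not check the shape of modification unless it is interacted with intervention, and even then the check has low power. The extra terms would recur for each outcome, and the plan has no formal multiplicity control. Both points stand as costs of the remedy.

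**Conclusion.** The point holds as an improvement to the plan. The hypothesis is framed only through a cut at 25, no intervention-by-BMI term is specified, and the data for a better test are already collected.

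Under normal BMI, 50-85% above 25 and linear modification, the cut loses about 36-57% of the information, and 80% power becomes about 45-61%. The lognormal cases with SD 6 and means 26-31 give about 40-66%. If the true effect is a step at 25, the cut loses nothing and continuous BMI is the weaker test. The range is an illustration under stated assumptions, not a property of this sample.

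The split is not an internal error, and the main Aim 1 and Aim 2 comparisons are unaffected.

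**What to change.** In the Aim 1 models, prespecify sales ban by baseline BMI and counseling by baseline BMI, with BMI continuous and centred, as the test of BMI modification. In the Aim 2 models, add the corresponding three-way term (sales ban by counseling by BMI), labelled exploratory. Check shape with one nonlinear BMI term that is itself interacted with intervention. Report the above-25 versus 25-or-below contrast alongside, to answer the hypothesis as worded.

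The change is to analysis-plan wording and needs no new data, visits or participants. Its costs are a linearity assumption that the shape check can test only weakly, lower power than the cut if there is a true step at 25, and a few more model terms per outcome.

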INSTITUTIONAL REVIEW BOARD**

Protocol Summary Form

counseling interventions, all found decreases in SSB consumption and BMI.⁴¹⁻⁴⁴ A pilot study and current trial by this team found that workplace sales bans reduce SSB consumption, waist circumference and some blood biomarkers for metabolic disease.¹¹

Analyses for all aims will also consider the hypothesis that those at highest risk for obesity and metabolic disease will benefit more from the interventions. This is justified by our pilot study showing that employees with a baseline BMI <25 benefitted most from the sales ban and brief intervention.¹¹ Preliminary studies (described above) suggest that ethnic minority and lower occupational status employees may experience disproportionate reductions in SSB consumption following an employer sales ban.

Analyses for all aims will also consider the possibility that study participants exposed to the interventions could compensate for reduced SSB consumption during work hours by increasing their consumption of SSBs at home, or by increasing calories from sugary foods or in the total diet.^{107,108} In our evaluation of the UCSF sales ban, we observed no compensatory at-home SSB consumption but rather, spillover effects of the intervention: After 12 months of exposure to a sales ban, the average SSB intake of heavy drinkers not only declined at work but also by 40% at home (by 9.3 oz/day) (data unpublished).

Research Design for Aim 1: The main analysis will focus on ANOVA and regression modeling to determine the independent effects of each intervention on primary and secondary outcomes.

Key Measures for Aim 1: As described in section C3d above: HOMA, waist circumference, abdominal adiposity, SSB consumption, insulin sensitivity, BMI, lipid profile, triglycerides, triglycerides:HDL ratio, liver function, glucose control, demographics, risk factors/disparities, and intervention assignment.

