Power Calculations: Power calculations are based on changes observed in the pilot study and response rates from the current Sutter Health trial. Calculations are conservative, based on 80% retention of participants after 12 months. With an initial N of 700 drawn from 16 Sutter Health sites randomly assigned to the sales ban and control conditions, and with participants within those sites randomly assigned to brief intervention/no brief intervention conditions, 80% retention would result in an overall N of 550 at 12 months. This results in approximately 138 in each of four experimental conditions: brief intervention + sales ban, the brief intervention only, sales ban only, and no intervention. Power analysis for a full factorial design conducted with the BDEsize¹⁰⁹ package within R¹¹⁰ indicates that with 80% power and an alpha level of .05, we will be able to detect effect sizes as small as .08 for the effect of each intervention on each outcome.

Anticipated Problems and Alternative Approaches: One potential problem is attrition, particularly biased attrition. We have calculated the sample to allow for up to 20% attrition; this is a conservative number based on our current Sutter Health data. In the UCSF pilot, which took place entirely pre-pandemic, we achieved a 94.4% response rate for blood draws. The existing study team has experience with the challenges of retaining a sample of health care workers during a challenging time and can use the same techniques (e.g., email and phone outreach) to reduce attrition here. We will conduct statistical tests to determine if attrition is biased on baseline risk levels, demographic factors (including regional differences), or study condition.

As with all self-report data, the survey data on SSB consumption could be biased, perhaps particularly for intervention participants who want to self-present improvement. However, the anthropometric and blood measures are objective and should show a consistent pattern with the SSB changes. Standard data cleaning procedures should reveal any extreme cases of self-representation bias. For SSB consumption data, we have also established a convention in previous studies of pruning outliers that are more than 4 SD away from the mean to reduce error from participants who may have responded inaccurately.

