Analytic Plan for Aim 2: Having established the main effects of each intervention under Aim 1, our analyses for Aim 2 focus on the interaction between them. Specifically, we anticipate that the combined intervention will have an effect above and beyond the simple additive effects of the two interventions. This analysis will require replicating the ANOVA and regression models used for Aim 1 with the addition to each of an interaction term for the two interventions. For example, the model predicting HOMA change will include assignment to the sales ban condition (coded as 0/1), assignment to the brief intervention condition (coded as 0/1), the interaction term for the two conditions (sales ban*brief intervention), baseline HOMA, baseline SSB consumption, baseline BMI, race/ethnicity, job classification (if sample size allows, as above), and sex. The procedure for analyzing each outcome is the same, but with each primary and secondary outcome substituted for HOMA in turn. This time, the main variable of interest will be the interaction term. We will graph and deconstruct each significant interaction term to determine the details of the interaction.

Power Calculations: As with Aim 1 above, power calculations are based on findings from the UCSF pilot and retention rates from the Sutter pilot. We will have 175 participants in each of the following groups. With 80% retention, this allows a final N of 550, with approximately 138 in each of the four experimental conditions. Power analysis for a full factorial design conducted with the BDEsize¹⁰⁹ package within R¹¹⁰ indicates that at 80% power and an alpha level of .05 we will be able to detect effect sizes as small as .12 for the interaction between the two interventions.

Anticipated Problems and Alternative Approaches: As with Aim 1, attrition and self-report bias are the primary potential issues we anticipate; handling of each is described above.

Expected Outcomes: We anticipate a significant interaction term, and more specifically, that the effect of the sales ban and brief intervention together will be stronger than each is individually. Participants assigned to the brief intervention and working at sites with a sales ban would thus demonstrate the greatest amount of change, and more change than one would expect if the effect of the two conditions were simply additive.

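### The sales ban is randomised by campus (8 vs 8), but its main analysis treats employees as independent and has no campus term

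*Combined protocol and SAP*

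**What the plan says.** Section 1 sets the unit of randomisation for the ban: "We will first cluster-randomize 8 Sutter Health hospital campuses to the SSB sales ban condition and 8 campuses to serve as controls". Section 4b (Participant Randomization) assigns counselling to individuals, stratified by location.

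Section 4c, Research Design for Aim 1, states: "The main analysis will focus on ANOVA and regression modeling to determine the independent effects of each intervention on primary and secondary outcomes". The Analytic Plan then describes an ANOVA on group means and a linear regression. The example model for HOMA change contains the two 0/1 assignment variables, baseline HOMA, baseline SSB consumption, baseline BMI, race/ethnicity and sex. All other outcomes follow the same procedure. No campus random effect, cluster-robust error, campus-level test or permutation test is named.

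The same section addresses site in three clauses:

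- The only model with a site level is introduced for counselling: "we will also analyze the effects of the brief intervention via an exploratory mixed regression model, with individuals nested within sites".
- The reason given for leaving site out of the main models is this: "Although we believe our strategy of cluster randomization and controlling for individual differences that can vary regionally (such as ethnic distribution) is sufficient".
- On what follows if site turns out to matter, the plan says: "If it is, we will consider mixed models where possible".

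Aim 2 reuses these models with an added interaction term, and says of it: "This time, the main variable of interest will be the interaction term". Section 1 also promises group comparisons under Aim 2: "We will compare outcomes for participants exposed to the multilevel intervention", against each of the other three groups. The Aim 3 mixed models nest day within study period within person, with no campus level. Neither power section gives an ICC or a design effect.

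**The concern.** The plan relies on cluster randomisation plus individual covariates. Cluster randomisation is what makes campus the unit of replication for the ban: there are 16 independent assignments, not about 550. Individual covariates remove campus correlation only as far as they explain differences between campuses. Shared cafeterias, local beverage supply and workforce culture need not be captured by BMI, sex or ethnicity.

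The exploratory site model is directed at counselling, which is compared within campuses. The follow-up clause could be read to cover the ban, but it gives no criterion for site being important and does not commit to using the mixed model.

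The stake is every contrast made across campuses: the ban main effect, ban-only vs none and ban-only vs counselling-only (Aim 1), and combined vs counselling-only and combined vs none (Aim 2). The ban's effect on waist circumference and HOMA is an Aim 1 hypothesis. Under Expected Outcomes, the plan would read significant main effects as evidence that each intervention works.

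**Working it through.** **Inputs.** From the documents: 16 campuses, 8 per arm; 700 enrolled; 550 analysed at 12 months (the plan's figure; 80% of 700 is 560, a small difference); alpha .05, taken as two-sided. Mean campus size is m = 550/16 = 34.4. Assumed: a residual ICC (after covariates) of 0 to 0.05, because the documents give none.

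**The plan's own figure.** Section 4c says "we will be able to detect effect sizes as small as .08 for the effect of each intervention on each outcome". For independent employees, 275 vs 275, two-sided .05 and 80% power, the detectable difference is d = 2.80 × √(4/550) = 0.239, or Cohen's f = 0.120. The stated .08 is not reproduced: read as f it has 46.5% power, read as d it has 15.5%. No metric is given, so .08 cannot be called wrong and is not used further. The calculation below starts from d = 0.239.

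**Design effect.** DE = 1 + (m − 1) × ICC = 1 + 33.4 × ICC. The true standard error of the ban effect is √DE times the one reported.

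**False-positive rate of the planned ban test.** 2 × [1 − Φ(1.96/√DE)].

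| Assumed ICC | DE | √DE | By formula | Simulated, individual-level | Simulated, campus-mean t-test (14 df) |
|---|---|---|---|---|---|
| 0 | 1.00 | 1.00 | 5.0% | 5.1% | 5.1% |
| 0.005 | 1.17 | 1.08 | 7.0% | 6.9% | 4.8% |
| 0.01 | 1.33 | 1.15 | 9.0% | 8.6% | 5.1% |
| 0.02 | 1.67 | 1.29 | 12.9% | 13.5% | 5.3% |
| 0.05 | 2.67 | 1.63 | 23.0% | 22.6% | 4.8% |

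The simulation used 10,000 null trials per ICC: 550 people in 16 campuses of 34–35, 8 vs 8, counselling balanced within campus, a normal outcome with a campus intercept, no covariates and no strata. With unequal campuses (8 of 17 and 8 of about 52; 6,000 trials), the individual-level rates at ICC 0.01 / 0.02 / 0.05 were 9.5% / 14.6% / 26.4%.

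**Four-group contrasts across campuses.** Each cell has about 17.2 people per campus, so DE = 1 + 16.2 × ICC = 1.16 / 1.32 / 1.81 at ICC 0.01 / 0.02 / 0.05. The same formula gives 6.9% / 8.8% / 14.5%. Simulated ban-only vs none: 7.0% / 9.1% / 14.3%.

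**Effects that are not inflated.** Under a shared campus intercept, the simulated false-positive rate was 4.9% / 4.8% / 4.4% for counselling and 4.8% / 5.0% / 4.3% for the interaction. This does not cover counselling effects that vary by campus.

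**Would the fallback protect the ban test?** The plan defines no rule. Suppose a 5% F-test for site within ban arm, with an automatic switch to the campus-mean test when it is significant. At ICC 0.01 / 0.02 / 0.05 the site test is significant in 22% / 45% / 86% of trials. The resulting ban false-positive rate is 7.2% / 8.4% / 6.2%. It is better than no switch, but above 5% at all three ICCs, and the plan does not commit to it.

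**The case against.** The strongest objection is that the campuses are randomised within strata of location (urban or rural) and number of employees (section 4b), which the simulation above ignores. Stratification balances part of the campus variation between arms, so 1 + (m − 1) × ICC overstates the ban's variance whenever the strata explain some of it. The documents give neither the number of strata nor how much they explain. Assuming four strata of four campuses that explain half the campus variance, the individual-level ban test rejects 6.9% / 8.7% / 14.2% at ICC 0.01 / 0.02 / 0.05 (a second simulation gave 6.6% / 8.6% / 15.2%). With an automatic pre-test switch the rate is 5.5% / 5.5% / 4.1%. An unstratified campus-mean test then becomes conservative, at 3.9% / 3.2% / 2.6%. This stands as a point about size and about how the remedy should be built. It does not remove the inflation from the analysis as planned.

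Two further points are fair. The true residual ICC may be small, and at zero there is no inflation. And 23% at ICC 0.05 requires the team to disregard a site effect that a 5% test would usually detect. The pre-test used here is an assumed procedure, not one the plan states. But the plan gives no basis for an ICC of zero, and at the smaller ICCs a pre-test mostly misses the clustering.

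**Conclusion.** The concern holds. The main analysis uses the wrong unit for the ban, no other section repairs it, and the stated justification does not answer the problem. With no stratum effect, a nominal 5% ban test has a false-positive rate of about 9% / 13% / 23% at ICC 0.01 / 0.02 / 0.05. It is about 7% / 9% / 14–15% if the strata explain half the campus variance, and 5% only if the residual campus correlation is zero or fully absorbed by the strata. The direction is certain for any positive residual ICC. The size depends on assumed values. The counselling effect, combined vs ban-only, and the Aim 2 interaction are compared within campuses and are not inflated by a shared campus intercept. This must be fixed, because the ban is one of the trial's two randomised interventions.

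**What to change.** 1. Make the main analysis of every cross-campus contrast cluster-aware from the start, with no pre-test. Use a linear mixed model with a campus random intercept and small-sample degrees of freedom (about 14 for the ban), plus a participant intercept if the 6- and 12-month visits are pooled. A campus-level test or a permutation test over the 16 campuses would also be valid. A fixed campus effect would not work, because it is fully confounded with the ban.
2. Preferably include the section 4b strata in the model, and permute within them if a permutation test is used.
3. Delete the statement that the present strategy is enough and the conditional clause about considering mixed models.
4. Restate the ban's detectable effect in the Aim 1 power section, with a named effect-size metric and a design effect over a stated ICC range.

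**Cost.** No new data are needed. The figures below ignore the strata, so they may be pessimistic. The interval ratio is √DE × t(14)/t(547) = √DE × 2.145/1.964. The detectable d is 3.01 × √(4 × DE/550), where 3.01 is the noncentrality giving 80% power on 14 df.

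| Assumed ICC | Ban interval wider by | Power at d = 0.239 | Detectable d at 80% power |
|---|---|---|---|
| 0.01 | 26% | 62% | 0.30 |
| 0.02 | 41% | 52% | 0.33 |
| 0.05 | 78% | 36% | 0.42 |

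Even at ICC 0, using 14 df raises the detectable d from 0.24 to 0.26. The ban comparison may therefore prove underpowered. That loss comes largely from having 16 campuses; the present analysis does not show it.
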